4.2 Sample Size Determination

For the primary objective, a failure is recorded if the subject’s plasma glucose fails to rise above 70.0 mg/dL (3.88 mmol/L) and fails to increase by at least 20.0 mg/dL (1.11 mmol/L) within 30 minutes of the decision to administer the dose of glucagon.

In this study, it is expected that the recovery (cure rate) will be high and approaching 100%. Since this is a cross-over design and each subject will serve as his/her control, power is improved.

The sample size was derived for 80% power of detecting non-inferiority with respect to the Odds Ratio of subject recovery rates at an alpha of 0.025 under a cross-over design. Based on an underlying Odds Ratio of 1.0, and rates of 0.20 versus 0.25, 111 subjects are required for the study. With an anticipated 10% drop-out rate, the total sample size for the study is 122 randomized subjects.

If there are subjects who are enrolled, but fail to be randomized, compensatory enrollment may be utilized to achieve at least 122 subjects who are randomized for the study. Once a subject is randomized, the subject will be analyzed for the study.

4.3 Randomization

Subjects who meet all eligibility criteria, who reach the baseline euglycemia steady state, and who the Investigator deems appropriate to begin the induction procedure at the first treatment visit will be randomized for the study.

The randomization schedule will be produced by the Study statistician a priori for loading and implementing in the Interactive Web-based Randomization System (IWRS). Using a permuted random block assignment, stratified by site, subjects will be randomly assigned to receive either Treatment Sequence 1 (G-Pen → GlucaGen Hypokit) or Treatment Sequence 2 (GlucaGen Hypokit → G-Pen).

4.4 Unblinding

This is a single-blind study. Only the subjects are blinded for treatment. The investigator and clinical staff will be aware of the treatment. Thus, there is no unblinding requirements needed for the study.

In the event that a subject is inadvertently unblinded during one or both of the treatment sequences, the investigator will note the event as a protocol violation, and the subject will be allowed to continue further study treatments as per the protocol.

At the end of the study, the subjects will be asked to guess what their first treatment was, and what their second treatment was from the choices of “Xeris Glucagon, G-Pen, administered by auto-injector” or “Comparator Glucagon, GlucaGen Hypokit, administered by needle and syringe”. The subject’s responses will be recorded in the electronic Case Report Form (eCRF) for the Subject Study Drug Assignment Questionnaire.

4.5 Changes in the Conduct of the Study

There were no changes in the conduct of the study at the time of preparing this statistical analysis plan.

5 STATISTICAL AND ANALYTICAL PROCEDURES

5.1 Analysis Populations and Treatment Groups

The following populations will be considered for the study:

5.1.1 Intent-to-Treat Population (ITT)

The Intent-to-Treat (ITT) population is defined as all subjects randomized. A subject’s randomized treatment will be used for analysis regardless of the actual treatment received. ITT population will be used for all summaries except safety/tolerability and disposition (where Enrolled population will be used). Primary endpoint comparison and secondary efficacy analysis will be performed for ITT, mITT and PP populations.

5.1.2 Modified Intent-to-Treat Population (mITT)

The Modified Intent-to-Treat (mITT) population is defined as all ITT subjects and received at least one dose of study drug. The actual treatment received will be used for analysis.

5.1.3 Per-Protocol Population (PP)

The Per-Protocol (PP) population is defined as all randomized patients who during both study periods successfully receive a dose of both study drugs (G-Pen followed by GlucaGen Hypokit or GlucaGen Hypokit followed by G-Pen) and have no any major protocol deviations. The actual treatment received will be used for analysis.

Primary endpoint comparison and secondary efficacy analyses will be performed for ITT, mITT and PP populations.

5.1.4 Safety Population

The safety population is defined as all subjects randomized that received at least one dose of study drug. The actual treatment received will be used for analysis. The safety population will be used for all safety analyses and endpoints.

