At any time, the induction procedure may be terminated at the Investigator's discretion. If the procedure is terminated, appropriate measures (oral or IV glucose) will be administered at the Investigator's discretion. If a subject exhibits signs of coma or convulsions, a IV bolus dose of dextrose will be given per standard of practice. Signs and symptoms should be monitored, and if the subject's condition fails to improve in a timely manner, additional dextrose or other medical interventions may be given at the Investigator's discretion.

Note: Study glucagon should NOT be administered as hypoglycemia rescue in this context.

Euglycemia will be confirmed and the subject should be medically stabilized per Investigator discretion before being released. The treatment visits should be rescheduled after a minimum 3-day wait.

If an SAE occurs during hypoglycemia induction, the procedure will end, and IV insulin will be safely withdrawn. Causality should be fully assessed by both the Investigator and the Sponsor.

Note: subjects will undergo a maximum of 4 hypoglycemia inductions in this study to achieve two successful procedures.

Table 4 Insulin Dose Adjustments

Plasma Glucose		Measurement Interval (minutes)	Target Rate of Plasma Glucose Decrease	Insulin Bolus Criteria	Insulin Basal Rate Adjustment Criteria
(mg/dL)	(mmol/L)				
> 80	> 4.44	10	> 0.5 mg/(dL·min) (> 0.03 mM/min)	If plasma glucose ↓ < 0.15 mg/(dL·min) (< 0.01 mM/min); give 1 bolus	If plasma glucose ↓ < 0.5 mg/dL·min (< 0.03 mM/min), ↑ 20% (10 min)
66-80	3.66-4.44	5	0.33-0.5 mg/(dL·min) (0.02-0.03 mM/min)	If plasma glucose ↓ < 0.15 mg/(dL·min) (< 0.01 mM/min); give ½ bolus	If plasma glucose ↓ < 0.33 mg/dL·min (< 0.02 mM/min), ↑ 20% (10 min)
					If plasma glucose ↓ > 0.5 mg/dL·min (> 0.03 mM/min), ↓ 20% (10 min)
61-65	3.39-3.61	5	0.25-0.33 mg/(dL·min) (0.014-0.02 mM/min)	Not allowed	If plasma glucose ↓ < 0.25 mg/dL·min (< 0.01 mM/min), ↑ 20% (10 min)
					If plasma glucose ↓ > 0.33 mg/dL·min (> 0.02 mM/min), ↓ 20% (10 min)
54-60	3-3.33	5	0.15-0.25 mg/(dL·min) (0.008-0.014 mM/min)	Not allowed	If plasma glucose ↓ < 0.15 mg/dL·min (< 0.008 mM/min), ↑ 20% (10 min); or If insulin infusion rate was previously set to baseline or the insulin infusion rate was ↓ by 50%, then set new insulin infusion rate at 120% of the prior rate (5 min) Note: This escalation in rate can be performed every 5 minutes until the rate of decrease is > 0.15 mg/dL·hr (> 0.008 mM/hr)

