5.3.6.3 Safety Variables

All Safety and Tolerability assessments will be performed using the Safety Population.

5.3.6.3.1.1 Adverse Events (AE)

All verbatim AE terms will be coded using the Medical Dictionary for Regulatory Activities (MedDRA, latest version) and summarized by System Organ Class (SOC) and Preferred Term (PT). AE collection will begin from the time of informed consent.

Time periods for Adverse Events

Adverse Events will be attributed to analysis phases and periods by time of onset.

Treatment Emergent Adverse Events (TEAEs) will be defined as AEs not present prior to the start of study procedures, or AEs present before study medication that worsened after starting of study procedures at Day 1 prior to first dose administration. If a partially missing date or time of onset allows the possibility that an AE may be a TEAE it will be assumed that it is a TEAE.

TEAEs will be analyzed by treatment and in overall. TEAEs will be attributed to study treatment which was administered before the AE onset within the respective Treatment Period 1 or 2.

Each TEAE will be attributed to Treatment Period 1 or 2. If TEAE started at the time of Day 1 Pre-dosing procedures of second dose, it will not be attributed to Treatment Period 1, but will be counted in the Overall TEAE summary.

AEs will be summarized by treatment, period and in overall by the number and percentage of subjects who experienced at least one AE of the following categories in each treatment group: any AE, any AE from CRC admission to the time of induction, any AE from time of induction to treatment, any TEAE, any drug related TEAE, any severe or life-threatening TEAE, any serious TEAEs, any drug-related SAE, any SAE leading to death, any TEAE leading to study discontinuation, and any SAE leading to study discontinuation.

AEs will be tabulated by SOC and PT in each category.

TEAEs will be summarized by highest relationship to study drug (Not Related, Related) and maximum severity (Mild, Moderate, Severe). If severity of AE is missing, then the AE will be analyzed as 'Severe'. If relationship to study drug for the AE is unknown, then the TEAEs will be classified as Related, and non-TEAEs will be classified as Not Related.

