14.3.1.6.1	Summary of Treatment-Emergent Adverse Events Leading to Study Discontinuation by System Organ Class, Preferred Term and by Treatment (Safety Population)
14.3.1.6.2	Summary of Treatment-Emergent Adverse Events Leading to Study Discontinuation by System Organ Class, Preferred Term, Period and by Treatment Sequence (Safety Population)
14.3.2.1	Listing of Deaths (Safety Population)
14.3.2.2	Listing of Serious Adverse Events (Safety Population)
14.3.2.3	Listing of Treatment-Emergent Adverse Events Leading to Study Discontinuation (Safety Population)
14.3.4.1.1	Summary of Clinical Chemistry Results (Safety Population)
14.3.4.1.2	Summary of Clinical Hematology Results (Safety Population)

Tables	
Number	Title
14.3.4.3	Incidence of Abnormal Laboratory Findings (Safety Population)
14.3.5.1	Summary of Local Tolerability – Subjective Injection Site Discomfort from VAS (Safety Population)
14.3.5.2	Summary of Local Tolerability – Subjective Injection Site Discomfort from Ordinal Pain Scales (Safety Population)
14.3.5.3	Summary of Local Tolerability – Draize Scale (Safety Population)
14.3.6.1.1	Summary of Prior Medications by Treatment (Safety Population)
14.3.6.1.2	Summary of Prior Medications by Treatment Sequence (Safety Population)
14.3.6.2.1	Summary of Concomitant Medications by Treatment (Safety Population)
14.3.6.2.2	Summary of Concomitant Medications by Treatment Sequence (Safety Population)
Listings	
Number	Title
16.1.7	Listing of Randomization (Intent-to-Treat Population)
16.2.1.1	Listing of Patient Disposition (All Patients)
16.2.1.2	Listing of Screen Failure and Inclusion / Exclusion Criteria Assessment (All Patients)
16.2.2.1	Listing of Protocol Deviations (All Patients)
16.2.2.2	Listing of Major Protocol Deviations (All Patients)
16.2.4.1	Listing of Patient Demographic and Baseline Characteristics (Safety Population)
16.2.4.2	Listing of Medical History (Safety Population)
16.2.4.3.1	Listing of Prior Medications (Safety Population)
16.2.4.3.2	Listing of Concomitant Medications (Intent-to-Treat Population)
16.2.5.1	Listing of Study Drug Administration (Intent-to-Treat Population)
16.2.5.2	Listing of Euglycemic Baseline and Hypoglycemia Induction (All Randomized Patients)
16.2.6.1.1	Listing of Dose Monitoring – Plasma Glucose (Intent-to-Treat Population)
16.2.6.1.2	Listing of Dose Monitoring – Pharmacodynamic Parameters (Intent-to-Treat Population)
16.2.6.2.1	Listing of Hypoglycemia Symptom Questionnaire (Intent-to-Treat Population)

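### The pre-dose adverse event rows and the death and SAE listings use a dosed-only population, so a subject whose first-period induction ends in an SAE or death and who is never dosed is missing from them

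*SAP*

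**What the plan says.** SAP 5.1.4 sets two conditions for the safety set, randomization and dosing: "The safety population is defined as all subjects randomized that received at least one dose of study drug". It then gives the set universal scope: "The safety population will be used for all safety analyses and endpoints". SAP 5.3.6.3 repeats this: "All Safety and Tolerability assessments will be performed using the Safety Population". Protocol 13.5 agrees on the dosing condition.

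SAP 5.3.6.3.1.1 lists the categories of the adverse event overview. Two of them fall before study drug: "any AE from CRC admission to the time of induction, any AE from time of induction to treatment, any TEAE". In SAP Appendix 1 the overview (Table 14.3.1.1) is labelled Safety Population. So are Listing 14.3.2.1, "Listing of Deaths (Safety Population", and Listing 14.3.2.2, "Listing of Serious Adverse Events (Safety Population". The general adverse event listing, 16.2.7, is labelled All Patients.

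Protocol 7.2, under Induction Termination, provides for the case at issue: "If an SAE occurs during hypoglycemia induction, the procedure will end, and IV insulin will be safely withdrawn". Protocol 7.3 permits study glucagon only in a confirmed hypoglycemic steady state. Protocol 12.3 collects adverse events from informed consent.

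**The concern.** The two early rows of the overview describe harm that arises before study drug. Their denominator, however, is made up of subjects who received study drug at some point. An event serious enough to end participation before any dose removes the subject from both numerator and denominator. The subjects most at risk of removal are those with the worst induction outcomes.

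Readers take listings of deaths and SAEs as complete for the trial. As labelled, these two need not be: a death during a first induction would not appear in the listing of deaths. The SAP is also uneven, since the general listing is wider than the two listings that matter more.

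Induced hypoglycemia is a deliberate exposure in this trial. Protocol 12.2 does not count it as an adverse event unless it is serious, so a serious event is how the hypoglycemia itself enters the adverse event data.

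**Working it through.** The plan states no figure on this point, so the check follows the population definition through each output.

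**Inputs**
- Membership: randomized and dosed at least once, at any visit (SAP 5.1.4).
- Scope: all safety outputs (SAP 5.1.4 and 5.3.6.3).
- Output labels: SAP Appendix 1.
- An induction SAE ends the procedure (Protocol 7.2). There is no dose outside steady state (Protocol 7.3).
- Terminated visits should be rescheduled, with at most four inductions per subject (Protocol 7.2). Subjects may also withdraw or be withdrawn for safety (Protocol 10.3).

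**Trace by type of subject**

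| Subject | Safety Population | Pre-dose rows of 14.3.1.1 | 14.3.2.1 / 14.3.2.2 | 16.2.7 |
|---|---|---|---|---|
| First induction ends in an SAE; rescheduled and later dosed | in | in | in | in |
| Dosed in period 1; SAE in the second induction | in | in | in | in |
| Randomized; induction SAE or death; never dosed | out | out | out | in |
| Induction SAE before randomization; never dosed | out | out | out | in |

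The fourth row depends on when randomization happens, and the documents conflict. Protocol 10.2.1.2 places it generally 30 to 60 minutes into induction, and SAP 4.1 also places it after the initial bolus has taken effect. Protocol 9.3.3 places it at the start of induction, and Protocol 8.3 and SAP 4.3 read similarly. The conclusion does not need this resolved, because the dosing condition alone excludes the subject.

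**Direction of the effect**

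Let e of the n subjects in the safety set have a pre-dose event, and let k never-dosed subjects with such an event be left out. The reported rate is e/n. With the k subjects restored it is (e + k)/(n + k). The difference is

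(e + k)/(n + k) − e/n = k(n − e) / [n(n + k)],

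which cannot be negative because e ≤ n. Leaving out subjects who had an event can therefore only lower the rate, and the event count can only be understated. Never-dosed subjects without an event also leave the denominator, which pulls slightly the other way. With m of them, the reported rate is too low whenever k/(k + m) exceeds e/n, that is, whenever pre-dose events are more frequent among the never-dosed than among the dosed. That is the likely pattern when the event is the reason for not being dosed.

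**Size**

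The documents give neither k nor m. The anticipated 10% drop-out (SAP 4.2) is not split into losses before and after the first dose. No numerical example can be anchored in the documents, so none is given.

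**The case against.** A safety set of dosed subjects is specified in the protocol, matches the SAP and suits a comparison of two drugs. The event is also recorded elsewhere. Listing 16.2.7 covers all patients, and SAP 5.3.6.3.1.1 gives the adverse event listings a seriousness flag and outcome. Disposition covers all enrolled subjects with reasons for discontinuation. Protocol 12.9 requires SAEs to reach the sponsor within 24 hours and deaths immediately. SAP 8 allows table names and structures to change. All of this stands and limits the point to one summary table and two dedicated listings. It does not explain why events that precede dosing should have a dosed-only denominator.

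Four stronger readings are tempting, and the documents do not support them.

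- *A serious induction event would vanish from the report.* It would not, because Listing 16.2.7 shows it.
- *SAEs are the only record of harm from induction.* Plasma glucose is measured throughout induction and symptoms are scored at each draw (Protocol 7.2 and 10.2.1.2). Listing 16.2.5.2 covers all randomized subjects. Listing 16.2.6.2.1 and Figure 14.2.4.1 cover the ITT population. Non-serious induction events other than hypoglycemia and injection site reactions remain reportable.
- *The overview counts only subjects who came through every induction.* One dose at any time is enough for inclusion, so most failed or interrupted inductions stay in.
- *The predecessor study shows that the problem is common.* Protocol 7.2 reports that about 30% of procedures in XSGP-301 fell below 40 mg/dL. That is a glucose reading, not an SAE rate, and the algorithm was later modified and then refined again. Protocol 6.4 reports no SAEs in either treatment group of XSGP-303, although a statement by treatment group does not settle what happened before dosing.

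**Conclusion.** The point holds within narrow limits. If the plan is followed as written, a subject whose first-period induction ends in an SAE or death and who is never dosed is absent from the two pre-dose rows of Table 14.3.1.1 and from Listings 14.3.2.1 and 14.3.2.2. Each such omission can only lower the pre-dose rates. The subject remains visible in Listing 16.2.7, and nobody who was dosed at any visit is affected. The primary analysis and the by-drug comparison do not change.

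The size is unknown and may be zero, since it requires at least one never-dosed subject with a pre-dose event. The conclusion assumes that the labels in SAP Appendix 1 are applied as printed. The change is still worth making, because it is cheap and listings of deaths and SAEs should be complete for the trial.

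**What to change.** 1. In SAP 5.1.4 and 5.3.6.3.1.1, exempt the two pre-dose categories from the Safety Population. Compute the admission-to-induction row on all subjects admitted to the research center for a treatment visit. Compute the induction-to-treatment row on all subjects who received the first induction insulin bolus, dosed or not. State each denominator in the table. A never-dosed subject has no actual treatment, so these subjects belong in the overall column.
2. In SAP Appendix 1, relabel Listings 14.3.2.1 and 14.3.2.2 to All Patients, matching 16.2.7. All Patients is safer than All Enrolled, because SAP 5.1 does not define an enrolled population.
3. Keep the dosed Safety Population for all by-drug summaries of treatment-emergent events.
4. Leave Listing 14.3.2.3 as it is until the two definitions of a treatment-emergent event are reconciled. SAP 5.2 says that events before the first administration are not treatment-emergent, while SAP 5.3.6.3.1.1 counts from the start of Day 1 study procedures. Under the first definition, widening that listing would add nothing.

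The cost is SAP wording and a population flag. No new data are needed, because adverse events are collected from consent. The downside is that pre-dose event rates may look slightly less favourable. The change concerns analysis populations only and alters no clinical procedure.

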5.1.5 Treatment groups

For summary statistics, subjects will be presented in two different ways, as applicable to the type of analysis:

- by planned treatment sequence of randomized subjects (GlucaGen Hypokit – G-Pen and G-Pen – GlucaGen Hypokit). This presentation and analysis will be used optionally

for descriptive outputs, but generally will not be used for analysis of the primary objective.

- by planned/actual treatment of subject in each treatment period (GlucaGen Hypokit and G-Pen). This presentation and analysis will be used for all primary and secondary endpoints, and optionally for descriptive outputs (disposition, demographics, etc.).

Planned treatment will be used for ITT population analyses and actual treatment received (by Period) will be used for mITT, PP and Safety population analyses.

5.2 Reference Dates, Analysis Periods, Analysis Visits, and Baseline

There will be two treatment periods defined and analyzed, which starts from study drug administration and the associated clinical phases associated, related with the pre-dose study procedure:

SCREENING/BASELINE, RUN-IN (1 and 2), TREATMENT PERIOD (1 and 2).

- SCREENING/BASELINE: analysis phase starts with Informed Consent, includes Day -1 check-in before first drug administration.

Baseline will be defined as the last assessment within this phase and used as the reference point for safety assessments across the study to each of the visits (laboratory data, ECG, physical examination, weight, temperature and respiratory rate).

- PRE-TREATMENT PERIOD 1: analysis phase will be assigned only if subject failed to achieve hypoglycemic steady state and study drug was not administered at the first treatment visit. It will start from first overnight monitoring to last check-in before first drug administration inclusively.

Baseline 1 will be defined as last assessment at Day -1 of Treatment 1 and will be used as the reference point for safety assessments within Treatment Period 1 (HR and BP).

- RUN-IN 1: analysis phase starts from Day 1 of Treatment 1 study procedures prior to first drug administration and continues until the first drug administration or study discontinuation, whichever comes first.
- TREATMENT PERIOD 1: analysis phase/period starts from first drug administration to check-in of the next treatment visit or study discontinuation, whichever comes first.
- PRE-TREATMENT PERIOD 2: analysis phase will be assigned only if subject failed to achieve hypoglycemic steady state and the subject's second study drug was not injected at the first treatment visit after the end of Treatment Period 1. The period will start from first overnight monitoring after the end of Treatment Period 1 to last check-in before second drug administration inclusively.

Baseline 2 will be defined as last assessment at Day -1 before Treatment 2 and used as reference point for safety assessments within Treatment Period 2 (HR and BP).

- RUN-IN 2: analysis phase starts from Day 1 of Treatment 2 study procedures prior to second drug administration and continues until the second drug administration or study discontinuation, whichever comes first.
- TREATMENT PERIOD 2: analysis period/phase starts from second dose administration to the end of study.

RUN-IN 1 and RUN-IN 2 analysis phases will include all interventions before dose injections, thereof:

- EUGLYCEMIC BASELINE 1 / 2.

The Euglycemic Baseline phase will be determined as time interval which starts from last 30 minutes of the baseline euglycemic steady state period, covering at least 3 scheduled consecutive plasma measurements in the target range at 0, 15, and 30 minutes used to confirm euglycemic steady state; and stops just before hypoglycemia induction with IV bolus push dose.

Euglycemic Baseline (1 and 2): to determine for the Hypoglycemia Symptoms Assessment scheduled at the end of this phase just before the IV bolus push dose of insulin, will serve as baseline to determine hypoglycemia symptoms relief and/or resolution within Treatment Period (1 and 2). If more than one assessment is performed in this time interval, then the last assessment of each hypoglycemia symptom or score will be selected for use as the baseline.

- HYPOGLYCEMIA INDUCTION (1 and 2). During the induction procedure the subject will enter a state of hypoglycemia through the administration of regular insulin diluted in normal saline within a controlled and monitored setting.

Hypoglycemic steady state (1 and 2): for Treatment Period (1 and 2) is confirmed if:

- penultimate plasma glucose measurement during hypoglycemia induction is < 54.0 mg/dL (< 2.78 mmol/L);
- last plasma glucose measurement during hypoglycemia induction is ≥ 42 mg/dL (≥ 2.33 mmol/L) and < 54 mg/dL (< 2.78 mmol/L); and
- 8-minute linearly extrapolated value from two last measurements of plasma glucose is ≥ 42 mg/dL (≥ 2.33 mmol/L).

Hypoglycemic Baseline (1 and 2). If the subject achieved hypoglycemic steady state then from the last of the last two plasma glucose readings during hypoglycemia induction to time of study drug administration will be defined as Hypoglycemic Baseline for the corresponding treatment period and will serve as baseline for the Primary Endpoint and Secondary Endpoints related to pharmacokinetic and pharmacodynamic characteristics within Treatment Period (1 and 2).

Assessments and Adverse Events with onset in TREATMENT PERIOD 1 or TREATMENT PERIOD 2 will be attributed to the actual treatment and analyzed respectively. Adverse

Events which started at RUN-IN (1 and 2) phase, will be treated as TEAE, but not attributed to forthcoming treatment. They will be attributed to the previous treatment period (or prior to first treatment administration and not categorized as treatment emergent).

Visit 2 and Visit 3 will be differentiated to Day -1 and Day 1 according to protocol and schedule of assessments. Analysis periods, visits, and baseline are summarized in the table below.

Table 3 - Analysis Periods and Visits

Analysis Phase/ Period	Analysis Subperiod (optional)	Analysis Visit	Protocol Visit/ Period	Baseline for period?
SCREENING - BASELINE	Screening	Screening, Baseline*	Visit 1	Overall
	Check-In 1 (CRC Admission)	Treatment 1 Day -1, Baseline 1*/Baseline*	Visit 2	Period 1, Overall
RUN-IN 1	Overnight monitoring	Treatment 1 Day 1	Visit 2	
	Euglycemic Baseline 1	Treatment 1 Day 1, Euglycemic Baseline 1*	Visit 2	Period 1
	Hypoglycemia Induction 1	Treatment 1 Day 1 (pre-dose measurements), Hypoglycemic Baseline 1*	Visit 2	Period 1
TREATMENT PERIOD 1 / TREATMENT PERIOD 1	Post treatment 1 measurements/ CRC discharge	Treatment 1 Day 1 (post-dose measurements)	Visit 2	
	Outclinic 1			
	Follow-Up (optionally)	Follow-Up (optionally)		
	Check-In 2 (CRC Admission)	Treatment 2 Day -1, Baseline 2*	Visit 3	Period 2
RUN-IN 2	Overnight monitoring	Treatment 2 Day 1	Visit 3	
	Euglycemic Baseline 2	Treatment 2 Day 1, Euglycemic Baseline 2*	Visit 3	Period 2
	Hypoglycemia Induction 2	Treatment 2 Day 1 (pre-dose measurements), Hypoglycemic Baseline 2*	Visit 3	Period 2
TREATMENT PERIOD 2 / TREATMENT PERIOD 2	Post treatment 2 measurements/ CRC discharge	Treatment 2 Day 1 (post-dose measurements)	Visit 3	
	Outclinic 2			
	Follow-Up	Follow-Up	Visit 4	

* Derived visit.

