12. SAFETY AND ADVERSE EVENT (AE) REPORTING

12.1. Definition of an Adverse Event

An AE is any untoward medical occurrence in a clinical investigation subject administered a pharmaceutical product and which is not necessarily required to have a causal relationship with this treatment. An AE can therefore be any unfavorable and unintended sign, symptom, or disease temporally associated with the use of a medicinal product, whether or not considered related to the medicinal product. Examples of AEs include:

- Abnormal test findings.
- Clinically significant symptoms and signs.
- Changes in physical examination findings which are untoward and deemed clinically significant by the Investigator.
- Allergy/hypersensitivity.

The criteria for determining whether an abnormal objective test finding may be reported as an AE are as follows:

- Test result is associated with accompanying symptoms.
- Test result requires additional diagnostic testing or medical/surgical intervention.
- Test result leads to a change in study dosing or discontinuation from the study. significant additional concomitant drug treatment or other treatment.
- Test result is considered to be an AE by the Investigator or Sponsor.

Repeat of a test based on an abnormal result in the absence of the above conditions does not constitute an AE. Any abnormal test result determined to be an error does not require reporting as an AE.

A TEAE is an AE that either commenced following initiation of study treatment or was present prior to study treatment but increased in frequency or severity following initiation of study treatment.

Standard medical terminology should be used in describing AEs. Informal descriptions should be avoided.

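### The SAP gives two opposite rules for adverse events that start in the second pre-dose run-in, and does not settle whether events before the first dose are treatment-emergent

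*SAP*

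**What the plan says.** SAP 5.2 divides the study into phases. Treatment Period 1 runs from the first injection to check-in for the next treatment visit. Run-in 2 covers the Day 1 procedures up to the second injection, including the insulin induction.

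On adverse events that start in a run-in, 5.2 first says "Events which started at RUN-IN (1 and 2) phase, will be treated as TEAE, but not attributed to forthcoming treatment". As to where such events go instead, its next sentence reads "They will be attributed to the previous treatment period". A bracketed remark in that same sentence then takes events before the first dose out of the treatment-emergent class.

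SAP 5.3.6.3.1.1 (Adverse Events) defines treatment-emergent events as "AEs not present prior to the start of study procedures". Its definition also takes in earlier events if they "worsened after starting of study procedures at Day 1 prior to first dose administration". It then says "Each TEAE will be attributed to Treatment Period 1 or 2". For an event that starts in the Day 1 pre-dosing procedures of the second dose, it adds that "it will not be attributed to Treatment Period 1, but will be counted in the Overall TEAE summary".

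Protocol 12.1 starts the clock later: "A TEAE is an AE that either commenced following initiation of study treatment". Its other limb, for events that existed before, likewise requires worsening after study treatment has begun.

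SAP section 2 says the SAP supersedes the protocol's statistical text and that substantial differences will be identified. SAP section 10 lists one difference only, the replacement of the mixed model by time-to-event analysis for timing parameters.

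**The concern.** Safety and tolerability are the trial's secondary objective, and the by-drug tables of treatment-emergent events are its main display. Two programmers who follow different sections of the SAP would produce different tables from the same data.

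Under 5.2, an event provoked by the second insulin induction is counted against the glucagon product injected at the previous visit, 7 to 28 days before. Protocol 6.4 describes glucagon as having an extremely short half-life, so that attribution has little pharmacological basis. It adds background noise to the comparison of the two products.

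The start of the treatment-emergent clock also matters for causality. SAP 5.3.6.3.1.1 classes a treatment-emergent event of unknown relationship as Related and a non-treatment-emergent one as Not Related. An event in the first run-in could therefore be counted as drug-related before any study drug had been given.

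**Working it through.** The plan states no adverse event rate for the induction phase, so there is no figure to reproduce. The check sets the texts side by side and then bounds the effect with assumed rates.

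**Step 1. The rules compared**

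| Event starts in | SAP 5.2 | SAP 5.3.6.3.1.1 | Protocol 12.1 |
|---|---|---|---|
| Run-in 1 (before the first dose) | Called treatment-emergent, then called not treatment-emergent; no drug | Treatment-emergent by definition; no drug, because none has been given | Not treatment-emergent |
| Run-in 2 (before the second dose) | Treatment-emergent; charged to the period 1 drug | Treatment-emergent; Overall only | Treatment-emergent; no rule on attribution to a drug |

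The run-in 2 row is a direct contradiction within the SAP. Section 5.2 also conflicts with its own calendar: it ends Treatment Period 1 at the next check-in, before run-in 2 begins, yet assigns run-in 2 events to that period.

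**Step 2. Which events are exposed**

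Protocol 12.2 does not count hypoglycemia as an adverse event unless it meets a serious criterion. What can move is therefore any other adverse event with onset in run-in 2, plus serious hypoglycemia.

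**Step 3. Upper bound on the by-drug effect under 5.2**

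Inputs:
- 122 randomized subjects (SAP 4.2).
- Approximately equal sequences (protocol 9.1), so 122/2 = 61 subjects for whom each drug is the previous drug.
- q, the fraction of subjects with a run-in 2 event. This is an assumption; the documents give none.

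Maximum addition to each drug's rate = (61 × q)/122 = q/2.

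| Assumed q | Extra subjects per drug, at most (61 × q) | Added points per drug, at most |
|---|---|---|
| 5% | 3.1 | 2.5 |
| 10% | 6.1 | 5.0 |
| 20% | 12.2 | 10.0 |

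Under 5.3.6.3.1.1 the addition to each drug is zero.

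**Step 4. Effect on a contrast**

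Assume true post-dose rates of 30% and 20%, q = 10%, and run-in 2 events independent of post-dose events. A run-in 2 event adds a subject to a drug's count only if that subject has no other event on that drug:
- First drug: 0.30 + 0.05 × (1 − 0.30) = 0.335
- Second drug: 0.20 + 0.05 × (1 − 0.20) = 0.240
- Ratio: 0.335/0.240 = 1.40, against 0.30/0.20 = 1.50
- Difference: 9.5 points, against 10

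Both rates rise by a similar amount, and the contrast shrinks toward no difference.

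**Step 5. Run-in 1**

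Neither SAP section assigns run-in 1 events to a drug. Their status changes only the overall treatment-emergent count and, through the unknown-relationship rule, the overall count of related events.

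**The case against.** The strongest defense is that the adverse event section already does nearly the right thing. It ties attribution to a drug given before onset within the same treatment period, and it keeps second pre-dose events out of Period 1. It also plans an overview category for events from induction to treatment, and all events are listed with period and start date. On this view the defect is one stray passage in 5.2. Adverse events are summarized by counts and percentages, and the primary analysis is untouched. In addition, the SAP is entitled to supersede the protocol, so a different definition is not in itself an error.

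Most of this stands, and it limits the size of the point. It does not remove it: nothing in the SAP says which section governs, the overview category does not decide what enters the by-drug tables by system organ class and preferred term, and the departure from protocol 12.1 is not declared as section 2 promises. The sentence that gives every treatment-emergent event a period is best read as a general rule followed by its exception, so no weight is put on it here.

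A reader might infer more than the documents support:
- **That each drug's rate rises by the full induction event rate.** Only run-in 2 events can move, and each drug is the previous one for about half the subjects, so the ceiling is q/2.
- **That the by-drug tables fill with induced hypoglycemia.** Protocol 12.2 excludes it unless serious.
- **That repeat inductions, up to four per subject, all feed the rule.** Failed induction visits fall in the separate Pre-treatment Period phases; the 5.2 sentence names only Run-in 1 and 2.
- **That any known contrast, such as nausea, is diluted by all induction events.** In the preferred-term tables only nausea starting in run-in 2 could dilute the nausea contrast.
- **That the rule favors one product.** With balanced sequences it does not.

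**Conclusion.** The point holds as an inconsistency that must be resolved before the safety tables are programmed. SAP 5.2 and 5.3.6.3.1.1 give opposite instructions for run-in 2 events, 5.2 contradicts itself on run-in 1 events, and the pre-dose start of treatment emergence departs from protocol 12.1 without being declared.

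The by-drug effect arises only if the 5.2 rule is programmed. Its size is at most q/2 per drug, where q is unknown; q of 5% to 20% gives up to 2.5 to 10 points. These figures rest on equal sequences and assumed event rates, and the worked ratio of 1.40 against 1.50 also assumes independent events. The direction is dilution of the contrast, with neither drug favored. Run-in 1 events affect overall counts only.

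**What to change.** - In SAP 5.2, delete the sentence that assigns run-in events to the previous treatment period, and keep the 5.3.6.3.1.1 rule. State that an event is attributed to a product only if its onset is after that product's injection and before the Day 1 procedures of the next treatment visit.
- Start treatment emergence at the first study drug dose, as in protocol 12.1, and remove the conflicting run-in 1 wording from 5.2. If the earlier start is kept on purpose, declare and justify it in SAP section 10, and say how the unknown-relationship rule applies to events before the first dose.
- Tabulate run-in events and events in failed-induction visits (the Pre-treatment Periods) in the already planned induction category and in the overall adverse event total, under neither drug.

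The cost is SAP wording and the matching table specifications. The SAP already assigns events to phases by time of onset, so no new data are needed.
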